4.5 STUDY ASSESSMENTS

The schedule of activities to be performed during the study is provided in Appendix 1 and Appendix 2. All activities should be performed and documented for each patient.

If a breakthrough bleed occurs outside of a hospital visit and requires treatment, collection of a blood sample should occur within 30 minutes—24 hours but no later than 48 hours after treatment for the bleed has been administered. In such a case, to avoid requiring patients to return to the study site for a blood draw, this sample collection may be performed by a mobile nursing (MN) professional at the patient's home or another suitable location to improve access and convenience for patients participating in the study. In addition, if a patient or caregiver needs assistance with injecting emicizumab correctly, emicizumab may be administered by a MN professional.

The Sponsor will select a healthcare company that will be responsible for providing MN services for participating sites (the MN vendor). The MN vendor is responsible for ensuring that all MN professionals are licensed, qualified, and in good standing, as per applicable regulations, and that appropriate background checks have been performed. If the investigator at a participating site determines that MN services are appropriate for a patient and the patient gives written informed consent to participate in MN visits, the MN network will communicate with the patient and the patient's site. MN visits will be scheduled on specified visit days, to allow for relevant assessments to be performed by the MN professional. The schedule of activities (see Appendix 1 and Appendix 2) will specify which assessments may be performed by an MN professional.

4.5.1 Informed Consent Forms and Screening Log

Written informed consent/assent for participation in the study must be obtained before performing any study-related procedures (including screening evaluations). Informed Consent/Assent Forms for enrolled patients and for patients who are not subsequently enrolled will be maintained at the study site.

All screening evaluations must be completed and reviewed to confirm that patients meet all eligibility criteria before enrollment. The investigator will maintain a screening log to record details of all patients screened and to confirm eligibility or record reasons for screening failure, as applicable.

Emicizumab—F. Hoffmann-La Roche Ltd 43/Protocol BO41423, Version 3

4.5.2 Medical History, Concomitant Medication, and Demographic Data

Medical history, including clinically significant diseases, procedures, use of alcohol and drugs of abuse within the past year, and medical allergies will be recorded at baseline. In particular, sites should record whether the patient has any history of prior ITI, anaphylaxis, or known thrombophilia. For female patients, fertility status, and menstruation and menorrhagia history data will be recorded at baseline. In addition, all medications (including prescription, over-the-counter, and herbal/homeopathic remedies and therapies) used by the patient within 4 weeks prior to enrollment will be recorded. All bleed information (i.e., start date, cause, type, location) during the 24 weeks prior to study entry should be documented.

Demographic data will include age, sex, and self-reported race/ethnicity. Race and ethnicity are standard data points in clinical trials conducted by Roche, collected as part of the demographics, as there is potential that diseases might affect racial groups differently.

4.5.3 Physical Examinations

A complete physical examination, performed at screening and other specified visits, should include an evaluation of the head, eyes, ears, nose, and throat, and the cardiovascular, dermatologic, musculoskeletal, respiratory, gastrointestinal, genitourinary, and neurologic systems. Any abnormality identified at baseline should be recorded on the General Medical History and Baseline Conditions eCRF. The HJHS (see Appendix 3) will be performed as part of physical examination as per the schedule of activities (see Appendix 1)

4.5.4 Vital Signs

Vital signs will include measurements of respiratory rate, pulse rate, and systolic and diastolic blood pressure while the patient is in a seated position, and temperature. Record abnormalities observed at baseline on the General Medical History and Baseline Conditions eCRF. At subsequent visits, record new or worsened clinically significant abnormalities on the Adverse Event eCRF.

4.5.5 Laboratory, Biomarker, and Other Biological Samples

Laboratory assessments will be performed as indicated on the schedule of assessments. On days of study drug administration, laboratory samples should be drawn before the administration of study drug. Deviations from the schedule of assessments of ± 2 days are acceptable; however, pre-dose PK and PD sample collection and drug administration should coincide.

Samples for the following laboratory tests will be sent to the study site's local laboratory for analysis:

- Hematology: WBC count, RBC count, hemoglobin, hematocrit, platelet count, and absolute differential count (neutrophils, eosinophils, basophils, monocytes, lymphocytes, other cells), mean corpuscular volume, mean corpuscular hemoglobin, mean corpuscular hemoglobin concentration, and RBC distribution width
- Chemistry panel (serum or plasma): sodium, potassium, glucose, BUN, creatinine, calcium, phosphate, magnesium, total and direct bilirubin, albumin, ALP, ALT, AST, LDH, and CPK
- Coagulation tests (aPTT, PT/INR)
- Pregnancy test

All women of childbearing potential (including those who have had a tubal ligation) will have a serum pregnancy test at screening and within 7 days prior to initiation of study medication, if applicable. Urine pregnancy tests will be performed at specified subsequent visits. If a urine pregnancy test result is positive, it must be confirmed by a serum pregnancy test.

The following samples will be sent to one or several central laboratories or to the Sponsor or a designee for centralized analysis:

- Plasma samples for PK analysis
- Plasma samples for immunogenicity assessment (ADA)
- Plasma samples for anti-FVIII antibody measurement (inhibitor titer)
- Plasma samples for PD biomarker assessments (FVIII activity, FVIII protein level, thrombin generation, and others as listed in Appendix 2).
- Plasma aliquot for assessment of fibrinogen, D-dimer, and PF1+2
- Plasma and serum samples for bone and joint biomarkers
- Blood sample for clinical genotyping

In the event of coagulation factor product treatment for breakthrough bleeds, plasma samples should be collected within 30 minutes–24 hours (but no later than 48 hours) of initial coagulation factor product administration and sent to the central laboratory (see below) for monitoring of emicizumab pharmacokinetics, fibrinogen, FVIII activity (bovine and human coagulation factor chromogenic assays), D-dimer, PF1+2, and thrombin generation (two triggering agents; see Section 3.3.5).

A blood sample for clinical genotyping will be collected at pre-dose on Day 1 (see Appendix 2). DNA obtained from blood may be analyzed for FVIII mutations and potentially other coagulation-related gene polymorphisms (see Section 3.3.5). If the sample is missed on Day 1, it can be collected at any other scheduled visit. Only one clinical genotyping sample is required per patient. If the patient gives consent, the remainder of the clinical genotyping samples (blood) and their derivatives (DNA) will be

Emicizumab—F. Hoffmann-La Roche Ltd 45/Protocol BO41423, Version 3

stored under the Research Biosample Repository (RBR) policy, otherwise the remainder will be destroyed.

For the pediatric population, assessments that require blood draws should be monitored closely to ensure that institutional mandates regarding total sample blood volumes are followed. In situations where no institutional guidance is available, the following limits should be used and have been included in the design of the sampling program: No more than 1% of the total blood volume should be taken at one time and no more than 3% of the total blood volume should be taken over a 30-day period (total blood volume is defined as 80–90 mL/kg [European Union 2008]). Thus, blood sampling timepoints and volumes follow the Ethics Committee (EC) guideline on Ethical Considerations for Clinical Trials on Medicinal Products Conducted with the Pediatric Population (European Union 2008). In situations where the total volume of blood drawn might exceed the limits stated above, clinical (safety) laboratory assessments should be prioritized. Any remaining permitted blood volume should be collected for PK and immunogenicity samples, followed by PD samples/safety biomarkers. Refer to the laboratory manual for detailed weight-based blood sampling guidelines.

In certain instances, blood draws, emicizumab administration, or other assessments may be performed by an MN professional (see Section 4.5).

For sampling procedures, storage conditions, and shipment instructions, see the Sample Handling Manual.

Unless the patient gives specific consent for his or her leftover samples to be stored for optional exploratory research or RBR (see Section 4.5.9), biological samples will be destroyed no later than 5 years after the final Clinical Study Report has been completed.

When a patient withdraws from the study, samples collected prior to the date of withdrawal may still be analyzed, unless the patient specifically requests that the samples be destroyed or local laws require destruction of the samples. However, if samples have been tested prior to withdrawal, results from those tests will remain as part of the overall research data.

Data arising from sample analysis, including data on genomic variants, will be subject to the confidentiality standards described in Section 8.4.

Given the complexity and exploratory nature of exploratory biomarker analyses, data derived from these analyses will generally not be provided to study investigators or patients unless required by law. The aggregate results of any conducted research will be available in accordance with the effective Sponsor policy on study data publication.

Emicizumab—F. Hoffmann-La Roche Ltd 46/Protocol BO41423, Version 3

4.5.6 Electrocardiograms

Single ECG recordings will be obtained at specified timepoints, as outlined in the schedule of activities (see Appendix 1), and may be obtained at unscheduled timepoints as indicated.

All ECG recordings must be performed using a standard high-quality, high-fidelity digital electrocardiograph machine equipped with computer-based interval measurements. Lead placement should be as consistent as possible. ECG recordings must be performed after the patient has been resting in a supine position for at least 10 minutes. All ECGs are to be obtained prior to other procedures scheduled at that same time (e.g., vital sign measurements, blood draws) and should not be obtained within 3 hours after any meal. Circumstances that may induce changes in heart rate, including environmental distractions (e.g., television, radio, conversation) should be avoided during the pre-ECG resting period and during ECG recording.

For safety monitoring purposes, the investigator must review, sign, and date all ECG tracings. Paper copies of ECG tracings will be kept as part of the patient's permanent study file at the site. The following parameters will be obtained (and reported by the instrument): uncorrected QT interval, RR interval, heart rate, QT interval corrected through use of Bazett's formula, QT interval corrected through use of Fridericia's formula based on the machine readings of the individual ECG tracings, PR duration and QRS interval, and T- and U-wave morphology.

Any ECG changes that are associated with symptoms or lead to a change in study treatment or concomitant treatment, or discontinuation from study treatment must be reported as an adverse event on the adverse event eCRF. The ECG may be repeated if investigator deems it appropriate. During the study, the Sponsor may request copies of ECGs to be submitted to the Sponsor or a Central Vendor. Centralized ECG reading and interpretations will not be performed unless safety concerns arise.

4.5.7 Clinical Outcome Assessments

PRO data will be collected through use of the following instruments: BMQ, CATCH, EmiPref, EQ-5D-5L, MBQ, and MD with the PBAC.

4.5.7.1 Data Collection Methods for Clinical Outcome Assessments

The BMQ, CATCH, EmiPref, and EQ-5D-5L will be collected electronically using two devices (BMQ collected at home on a handheld device given to the patient/caregiver; the other questionnaires collected at site on a tablet). In addition, for female patients of childbearing potential, the MBQ and MD with PBAC will be collected on paper. These instruments will be translated into the local language as appropriate.

For the BMQ data, the patient will be provided with a handheld device (see Section 4.5.7.3). The handheld device to capture bleed data, emicizumab use, and other hemophilia medication use during study treatment via the BMQ will be

Emicizumab—F. Hoffmann-La Roche Ltd 47/Protocol BO41423, Version 3

provided/performed/during the Week 1 visit at the study site and will be used by the patient for the duration of the study to enter bleed and medication data weekly at a minimum. Patients who withdraw from emicizumab treatment will continue to record bleeds and hemophilia medication administration until they complete the safety follow-up visit. For the collection of the CATCH, EQ-5D-5L, and EmiPref, a site-based tablet will be used.

The devices will be pre-programmed to enable the BMQ (see Section 4.5.7.3), CATCH, EQ-5D-5L, and EmiPref at each specified timepoint (see Appendix 1). The electronic device and instructions for completing the instruments electronically will be provided by the site staff. The data will be transmitted to a centralized database maintained by the electronic device vendor. The data will be available for access by appropriate study personnel. If the electronic data collection system becomes unavailable, the Sponsor may instruct sites to collect PRO data (bleed data, emicizumab use, hemophilia medication use, and HRQoL) on paper, and once electronic data entry is available, all information will need to be entered and submitted electronically.

For female patients of childbearing potential, the MBQ will be self-administered on paper at the site during the clinic visits on Day 1 and subsequently every 4 weeks. The MD with PBAC will be completed on paper by patients at home. The MD with PBAC will be given to patients on Day 1 and should be completed monthly on days of menstruation. The patient should return the completed MD with PBAC to the site personnel during the next clinic visit. All MBQ and MD data will be entered into the study database by site personnel.

PRO instruments will be self-administered at the clinic at specified timepoints during the study (see Appendix 1) and at home when appropriate. At the clinic, instruments will be administered before the patient receives any information on disease status, prior to the performance of non-PRO assessments, and prior to the administration of study treatment, unless otherwise specified.

Patients should be given the following instructions for completing PRO instruments at home:

- Patients should complete the instruments in a quiet area with minimal distractions and disruptions.
- Patients should answer questions to the best of their ability; there are no right or wrong answers.
- Patients should not obtain advice or help from others (e.g., family members or friends) when completing the instruments.

During clinic visits, PRO instruments should be administered as outlined below:

 Patients' health status should not be discussed prior to administration of the instruments.

Emicizumab—F. Hoffmann-La Roche Ltd 48/Protocol BO41423, Version 3

- Sites must administer the official version of each instrument, as provided by the Sponsor. Instruments must not be copied from the protocol.
- Sites should allow sufficient time for patients to complete the instruments, estimated to be 15 minutes at each specified visit.
- Sites should administer the instruments in a quiet area with minimal distractions and disruptions.
- Patients should be instructed to answer questions to the best of their ability; there
 are no right or wrong answers.
- Site staff should not interpret or explain questions, but may read questions verbatim upon request.
- Patients should not obtain advice or help from others (e.g., family members or friends) when completing the instruments.

4.5.7.2 Description of Clinical Outcome Assessment Instruments Comprehensive Assessment Tool of Challenges in Hemophilia

CATCH is a newly developed, validated instrument to measure the effect of hemophilia and its treatment on pediatric (aged 8-17 years) and adult patients (aged ≥ 18 years), and caregivers of pediatric patients (Regnault et al. 2019). The adult and pediatric versions of CATCH are composed of seven domains, and the caregiver version of CATCH is composed of two domains. Each domain constitutes a set of specific items and overall items that help to assess the overall impact of the disease on a given domain. The current versions of the CATCH can be administered electronically. The instructions for completion are within the body of the questionnaire to allow participants to complete it independently.

The adult version covers concepts including daily activity risk perception and impact (48 items), social activity risk perception and impact (22 items), recreational activity risk perception and impact (32 items+larger bank of additional items), work impact (10 items), preoccupation (10 items), treatment burden (8 items), and pain (5 items) (see Appendix 4). The pediatric version includes concepts of daily activity risk perception and impact (38 items), social activity risk perception and impact (16 items), recreational activity risk perception and impact (34 items+larger bank of additional items), school impact (11 items), preoccupation (3 items), treatment burden (7 items), and pain (2 items) (see Appendix 5). For recreational activities, patients only respond to those items that are relevant to them. On average, the adult and pediatric versions take 15–20 minutes to complete. The caregiver version comprises concepts related to preoccupation (13 items) and treatment burden (8 items), and takes approximately 5 minutes to complete (see Appendix 6).

The items in the CATCH versions are scored on ordinal scales (3–4 points for pediatric version, 4–5 points for adults and caregiver versions), with an 11-point numeric rating scale for pain. All CATCH raw scores are obtained by calculating the mean of the item scores for all items within the corresponding concept and applying a linear

Emicizumab—F. Hoffmann-La Roche Ltd 49/Protocol BO41423, Version 3

transformation. The transformed scores range from 0 to 100 scale with higher scores indicating higher perceived risk or effect.

EQ-5D-5L

The EQ-5D-5L is a validated, self-report, health status questionnaire that is used to calculate a health status utility score for use in health economic analyses (EuroQol Group 1990; Brooks 1996; Herdman et al. 2011; Janssen et al. 2013) (see Appendix 7). There are two components to the EQ-5D-5L: a five-item health state profile that assesses mobility, self-care, usual activities, pain/discomfort, and anxiety/depression, as well as a VAS that measures health state. Published weighting systems allow for creation of a single composite score of the patient's health status. The EQ-5D-5L takes approximately 3 minutes to complete and will be completed by patients 12 years of age and older. It will be used in this study for informing pharmacoeconomic evaluations.

Emicizumab Preference Survey

Patient preference will be assessed through the EmiPref (see Appendix 8 and Appendix 9). Patients and/or caregivers will be asked to report which treatment regimen they would prefer to continue to receive or administer after having been treated with or administered IV FVIII prior to study entry and SC emicizumab during the study. Patients and/or caregivers who express a preference will then be asked to identify which reasons may have influenced their decision and indicate the top three reasons for this choice. This assessment will be performed at Week 17 when patients have gained sufficient experience with SC injection of emicizumab, while still reliably recalling their experience with prior therapy.

Menstrual Bleeding Questionnaire and Menstruation Diary

For females with bleeding disorders, menorrhagia can further diminish their health-related quality of life (Shankar et al. 2008). Menorrhagia is defined subjectively as excessive or prolonged loss of blood on a regular cyclical basis or objectively as menstrual blood loss≥80 mL for the whole period (Higham et al. 1990).

All female patients of childbearing potential will be asked to complete two PROs, the MBQ and MD (See Appendix 13 and Appendix 14).

- The MBQ is a validated measure for menorrhagia and is widely used in research and clinical practice to assess impact on the menstrual bleed-related heaviness, pain, irregularity, and quality of life (Matteson et al. 2015). The MBQ is a 20-item measure covering four aspects regarding heavy menstrual bleeding: heaviness (8 items), quality of life (8 items), irregularity (1 item), and pain (1 item).
- The MD will use a PBAC, which has shown good correlation with menstrual blood loss (Higham et al. 1990). The PBAC is a chart that records the occurrence and size of clots, and the number of episodes of heavy bleeding (flooding), as well as depicts the amount of blood loss during a cycle. When summed, the weighted scores for light, moderate, or severe blood loss determine a PBAC score for each cycle.

Emicizumab—F. Hoffmann-La Roche Ltd 50/Protocol BO41423, Version 3

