2.2 EFFICACY OBJECTIVES

2.2.1 Primary Efficacy Objective

The primary efficacy objective for this study is to evaluate the efficacy of emicizumab on the basis of the following endpoint:

• Number of treated bleeds over time (i.e., bleed rate)

2.2.2 Secondary Efficacy Objectives

The secondary efficacy objective for this study is to evaluate the efficacy of emicizumab on the basis of the following endpoints:

- Number of all bleeds (i.e., those treated and untreated with FVIII) over time
- Number of joint bleeds over time
- Number of target joint bleeds over time (target joints are defined as joints with ≥3 bleeds occurring in the same joint during the last 24 weeks or unresolved target joints)

An unresolved target joint is defined as a target joint that does not fulfil the criterion of ≤ 2 bleeds into this joint within a consecutive 12-month period.

- Number of spontaneous bleeds over time (spontaneous bleed rate)
- Joint health, as assessed through use of the Hemophilia Joint Health Score (HJHS) at specified timepoints
- Health-related quality of life (HRQoL), as assessed through use of the Comprehensive Assessment Tool of Challenges in Hemophilia (CATCH) Questionnaire over time
- Preference for emicizumab compared with previous FVIII regimen, as assessed through use of the Emicizumab Preference Survey (EmiPref) at Week 17
- Effect of emicizumab prophylaxis treatment on physical activity compared with physical activity at baseline
- Effect of emicizumab prophylaxis treatment on menstruation heaviness and menstruation-related quality of life in female patients of childbearing potential, as assessed through the use of the Menstrual Bleeding Questionnaire (MBQ) and the Menstruation Diary (MD) with the Pictorial Blood Assessment Chart (PBAC) over time

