3. STUDY DESIGN

3.1 DESCRIPTION OF THE STUDY

Study BO41423 is a multicenter, open-label, single-arm study designed to evaluate the safety, efficacy, pharmacokinetics, and pharmacodynamics of emicizumab in patients with mild or moderate hemophilia A without inhibitors against FVIII. Four loading doses of emicizumab 3 mg/kg will be administered subcutaneously QW for 4 weeks followed by patient preference of one of the following maintenance regimens: 1.5 mg/kg QW, 3 mg/kg Q2W, or 6 mg/kg Q4W. The three maintenance dose regimens have shown equivalent average steady-state exposure, and demonstrated consistent efficacy and safety, and are approved in several countries for the treatment of Hemophilia A with or without FVIII inhibitors. As patients with mild or moderate Hemophilia A have residual FVIII levels of ≥ 1%, it is of interest to collect safety data over a longer time period. Therefore, in this study, the observation time to primary analyses was extended to approximately 52 weeks compared with prior Phase III studies investigating emicizumab.

Approximately 70 patients of all age groups will be enrolled, approximately 20 patients with mild (FVIII level between >5% and <40%) and approximately 50 patients with moderate (FVIII level between \geq 1% and \leq 5%) hemophilia A, without FVIII inhibitors whose phenotype warrants prophylaxis.

Emicizumab—F. Hoffmann-La Roche Ltd 28/Protocol BO41423, Version 3

Patients (or their legally authorized representative herein referred to as patient[s]) will choose the preferred emicizumab maintenance regimen (1.5 mg/kg SC QW, 3 mg/kg SC Q2W, or 6 mg/kg SC Q4W) after consultation with his or her treating physician. The chosen regimen needs to be maintained throughout the study until completion of at least 52 weeks.

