Appendix 1: Schedule of Activities (cont.)

- ⁿ If screening ECG is abnormal, repeat at Week 1. ECGs will also be performed: once during Weeks 4–8 and once 24 and 49 weeks after starting emicizumab.
- Pre-dose: WBC count, RBC count, hemoglobin, hematocrit, platelet count, and absolute differential count (neutrophils, eosinophils, basophils, monocytes, lymphocytes, other cells), mean corpuscular volume, mean corpuscular hemoglobin, mean corpuscular hemoglobin concentration, and RBC distribution width will be performed locally. Laboratory assessments completed at the screening visit do not have to be repeated at Week 1 if the period between screening and Week 1 is 5 days or less and there has been no change in health status as assessed by the investigator.
- Pre-dose: sodium, potassium, glucose, BUN, creatinine, calcium, phosphate, magnesium, total and direct bilirubin, albumin, ALP, ALT, AST, LDH and CPK will be performed locally. Laboratory assessments completed at the screening visit do not have to be repeated at Week 1 if the period between screening and Week 1 is 5 days or less and there has been no change in health status as assessed by the investigator.
- ^q All women of childbearing potential (including those who have had a tubal ligation) will be required to have a negative serum pregnancy test result at screening and within 7 days prior to initiation of study medication (Day –7 to Day –1). If applicable, urine pregnancy tests will be performed at the scheduled visits, except for Weeks 2–4. If a urine pregnancy test is positive, it must be confirmed by a serum pregnancy test. If the serum pregnancy test is positive, further administration of emicizumab should be discontinued.
- ^r Emicizumab may be administered by a mobile nursing professional.
- Bleed information for each bleed (start date and time, reason, type, location, and associated symptoms (only collected for muscle and joint bleeds in patients 12 years of age and older)) and medication for bleeds (breakthrough bleeds) should be reported by the patient via an electronic, handheld device when a bleed occurs or at least on a weekly basis (retrospective reporting for last 7 days). If the patient discontinues study treatment, bleed and bleed medication data should be provided by the patient until the safety follow-up visit (24 weeks after final study drug administration). Emicizumab doses should be recorded by the patient in the BMQ starting on Day 1.

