Appendix 14 Menstruation Diary

Study Number: Subject Number:
Site Number: Date of Study Enrollment:

Each row represents a day of the month. Please count the number of sanitary pads and/or tampons you used each day (24 hours period), if any. The light, medium, and heavy columns indicate how stained each item was with blood. If you used both a pad and tampon simultaneously and both sanitary items were stained with blood, please include both items in the diary.

If you passed any clots, please indicate this on the relevant days and the approximate size (small = close to the size of penny; large = close to the size of a quarter).

If you experienced any episodes of 'flooding' / overflowing / staining of clothing or underwear, please indicate the number of episodes on the relevant days.

If you also experienced bleeding between periods that required sanitary protection, please record the items on the relevant days.

Please do not write anything in the Score column.

Date	Pads			Tampons			Clots		Flooding Episodes	Score
	Light	Medium	Heavy	Light	Medium	Heavy	Small	Large		TO BE COMPLETED BY STUDY STAFF ONLY
1										
2		ļ.								
3										-
4		\\								
5								2		
6		k								
7										
8										
- 922										
10 11										
12										
14										
15										
16		4		4:						-
17										
18		1		-				-		
19										
20		/		1/2				2		
21		2								
22										
23									¢.	
24										
25								5 3		
26										
27										
28				· ·						
29		ř.		Ť ·						
30										
31

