3.3.2.4 Menstruation Heaviness and Menstruation-related Quality of Life

MBQ will be summarized descriptively over time, including change from baseline for individual subscales (heaviness, quality of life, irregularity, and pain) and total score. Pictorial Blood Assessment Chart (PBAC) scores will be summarized descriptively over time. If the number of female patients of childbearing potential is too low to provide reliable summaries, the data will be listed and presented in individual patient plots where applicable.

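### The PBAC diary is first issued on the day of the first emicizumab dose, so no pre-treatment PBAC score is planned and the before-and-after contrast for menstrual heaviness rests on the MBQ alone

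*Protocol*

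**What the plan says.** Protocol 2.2.2 lists as a secondary efficacy endpoint the "Effect of emicizumab prophylaxis treatment on menstruation heaviness and menstruation-related quality of life in female patients of childbearing potential", measured with the MBQ and the MD with PBAC. SAP 2.3.2 repeats it.

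On timing, Protocol 4.5.7.1 states "The MD with PBAC will be given to patients on Day 1 and should be completed monthly on days of menstruation" and "The MD with PBAC will be completed on paper by patients at home". Protocol 4.5.7.4 and Appendix 1 footnote u give the same rule, and the diary row in Appendix 1 reads monthly. No text asks for a diary during screening.

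Treatment begins on the same day. Protocol 3.1 says "Four loading doses of emicizumab 3 mg/kg will be administered subcutaneously QW for 4 weeks", and Appendix 1 footnote s says "Emicizumab doses should be recorded by the patient in the BMQ starting on Day 1". Section 3.1 also describes the study as single-arm.

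The PBAC score belongs to a menses. Protocol 4.5.7.2 says "the weighted scores for light, moderate, or severe blood loss determine a PBAC score for each cycle". For analysis, SAP 3.3.2.4 says only "Pictorial Blood Assessment Chart (PBAC) scores will be summarized descriptively over time". In the same paragraph it plans change from baseline for the MBQ subscales and total score. Protocol 6.5.2.2 draws the same distinction.

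**The concern.** With no control arm, the only way to describe an effect on menstrual heaviness is to compare each woman before and during treatment. The PBAC is the instrument that counts products, clots and flooding day by day, and the protocol cites it as correlating well with menstrual blood loss. It is named for an effect objective, yet its first record is made after dosing has started. Any early change would already be in the first score, and a flat line afterwards could mean either a prompt benefit or none.

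The SAP's fallback for small numbers is individual patient plots. For the PBAC, these would have no pre-dose point.

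**Working it through.** The documents give no sample size, power or precision for the PBAC, so there is no figure to reproduce. The main check is a comparison of dates. The percentages after it are illustrations that rest on assumptions.

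**Dates**
- Diary issued: Day 1 (Protocol 4.5.7.1, 4.5.7.4, Appendix 1 footnote u).
- First emicizumab dose: Day 1, with further loading doses on Days 8, 15 and 22 (Protocol 3.1, Appendix 1).
- Diary completed at home on days of menstruation, so after the Day 1 visit.
- Planned pre-treatment PBAC cycles per woman: 0.

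**Could another planned record supply the baseline?**
- Protocol 4.5.7.4 describes the diary as documenting product use over the past month. The next sentence issues it on Day 1 for use on days of menstruation, and the Appendix 14 form asks for daily counts. This does not create a retrospective score, though the wording should be tidied.
- Menstruation and menorrhagia history is taken at baseline (Protocol 4.5.2), but it is not a PBAC score.
- The Appendix 1 diary row also has an entry at safety follow-up. That visit is only for patients who discontinue, 24 weeks after the last dose. It is a post-treatment record, not a pre-treatment one.

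**Could the first diary menses serve as baseline?** Assume cycle length L and Day 1 falling uniformly within the cycle. The share of first diary menses that start on or after Day 8 is (L − 7)/L.

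**What would a screening diary capture?** Assume a menses of 5 days. A window of W days captures an onset with probability min(1, W/L), and a complete menses with probability min(1, (W − 5 + 1)/L). Screening lasts up to 4 weeks (Protocol 3.2), so W = 28 is the full window; W = 7 illustrates a short one.

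| L (days) | First diary menses on or after Day 8 | W = 28: onset | W = 28: complete | W = 7: onset | W = 7: complete |
|---|---|---|---|---|---|
| 21 | 14/21 = 67% | 100% | 100% | 7/21 = 33% | 3/21 = 14% |
| 28 | 21/28 = 75% | 100% | 24/28 = 86% | 7/28 = 25% | 3/28 = 11% |
| 35 | 28/35 = 80% | 28/35 = 80% | 24/35 = 69% | 7/35 = 20% | 3/35 = 9% |

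**Precision even with a baseline.** Protocol 3.1 hopes for at least 5 female patients. The 95% confidence half-width for a mean within-woman change is t(0.975, n − 1)/√n in units of its standard deviation. For n = 5 this is 2.776/2.236 = 1.24 SD; for n = 10 it is 2.262/3.162 = 0.72 SD.

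**The case against.** The strongest reply is that the objective is served by two instruments and one already has a proper baseline. The MBQ is completed in clinic on Day 1, before study treatment and with past-month recall. Its 8-item heaviness subscale covers soaked products, soaking through clothes and clots, and change from baseline is planned. That stands. A reader might infer that the menstruation endpoint has no baseline at all; the documents do not support this, and the point is confined to the PBAC.

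A second reply is that a pre-dose cycle would not establish cause. That also stands. SAP section 3 calls the study entirely descriptive, and one cycle in about 5 women settles nothing. Nor need that cycle be free of treatment. Prior emicizumab use is not an exclusion (Protocol 4.1.2), and regular FVIII prophylaxis may continue until the second loading dose (4.4.1). Hormonal methods are among the contraceptive examples in 4.1.1, and starting one at entry could itself change menses. A pre-dose score would give the plots a reference point, not attribution to emicizumab.

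A reader might also see a mismatch between scoring by cycle and a diary form on which "Each row represents a day of the month". This is not an error. The form is filled in daily, Protocol 4.5.7.2 scores by cycle, and menses start and end dates are recorded on the eCRF (Appendix 1 footnote u). Cycle totals can be formed whichever sheet the days fall on, and no text says scores are summed by sheet.

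The remaining reply is low practical weight: few women, one of many secondary endpoints, and listings or plots already foreseen. This limits the importance of the point but does not supply the missing score.

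**Conclusion.** The point holds for the PBAC. No pre-treatment cycle is planned, so in this single-arm study the PBAC can describe only level and trend on treatment, and the pre-to-on-treatment contrast rests on the Day 1 MBQ. This follows from the stated dates and needs no assumption. That the first diary is a poor substitute rests on uniform timing and assumed cycle lengths: 67% to 80% of first diary menses start on or after Day 8.

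The right phrase is no pre-treatment cycle. A claim that no untreated cycle is ever recorded would go too far, because women who discontinue have a diary entry at safety follow-up. It would be no substitute in any case: it exists only for those women, and Protocol 5.1.1.5 says effects on coagulation assays may persist for up to 6 months after the last dose.

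This is a cheap improvement of modest weight. With 5 women, even a PBAC with a baseline would have a half-width of about 1.24 SD for mean change.

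**What to change.** In Protocol 4.5.7.1, 4.5.7.4 and Appendix 1 (diary row and footnote u), issue the paper diary at consent or screening and ask women to record any menses before Day 1. Appendix 1 footnote e already allows consent more than 28 days before treatment, so the window can be longer than screening itself. Clarify the past-month wording in 4.5.7.4 at the same time, and align the copy of the schedule in SAP Appendix 2.

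In SAP 3.3.2.4, define the PBAC baseline as a complete pre-dose menses. Present change from baseline, or individual plots with the pre-dose point, for women who have one. Flag prior emicizumab use, ongoing FVIII prophylaxis and hormonal contraception during that cycle.

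The cost is a schedule entry, footnote and section wording, and a few lines of SAP text. The form is the same and no visit is added. The drawback is incomplete capture. Assuming a 28-day cycle, a full 28-day window yields a complete 5-day menses in about 86% of women, whereas a 7-day window yields even an onset in only about 25%. Women without a pre-dose menses would contribute on-treatment scores only, and the result stays descriptive.

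If the diary can no longer be added, state in SAP 3.3.2.4 that the PBAC is on-treatment description only, and rest any statement of effect on MBQ change from baseline.
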